1.2 Country Participation

All National Societies from the EHRA White Book and all other identified European Lead Extraction Centres have been invited to participate.

2 BACKGROUND AND RATIONALE

Background

The implant rate of Cardiovascular Implantable Electronic Devices (CIED) continues to rise in most countries. The number of leads per patient is increasing due to a higher proportion of dual versus single chamber devices and an increase of CRTP/D systems. Greater life expectancy, need for upgrade, multiple replacements of generators or pocket revisions for complications expose patients to infections.

Despite advances in technology and improvements in reliability, leads remain the weak point of the systems and in some cases may fail.

Transvenous Lead extraction is the gold standard in the treatment of CIED related infective complications and often required in the management of leads malfunction.

Initially NASPE and subsequently HRS and EHRA have published recommendations describing indications, settings, facilities, training and accreditation for transvenous lead extraction procedures.

Rationale

During the last 10 years transvenous lead extraction techniques have been improved, becoming more complete, sophisticated and efficient.

Recent advances in experience, tools, techniques and approaches in TLE have improved effectiveness and an increasing number of centers currently perform TLE procedures. Lead management requires a broad understanding of the pathophysiology of

mechanical and clinical issues associated with lead dysfunction, and a primary commitment to measuring outcomes and quality. A Survey able to characterize Centres performing TLE and to capture all the relevant clinical and procedural information of patients undergoing TLE may allow us to improve the knowledge of outcomes in real world clinical practice.

3 STUDY DESIGN AND METHODS

This is a prospective, multicentre, European Controlled Registry of consecutive patients undergoing TLE procedures in European Countries.

All consecutive patients will be enrolled per centre and followed up to 1 year.

Enrollment will start the day before the procedure.

Indications to perform procedures will be left completely to the decision of participating physicians.

No specific protocol or recommendations for the procedure, materials, techniques of lead extractions, or treatment after the procedure will be mandated during this observational study.

3.1 DURATION OF THE STUDY

It is anticipated that over 100 centres will participate in the registry. Each centre will register consecutive patients for a total of 3000 patients.

The study should commence recruitment of patients in October 2012 and finish in June 2013. In the event that less than 3000 patients are enrolled at that time the study can be continued until this number of enrollees is reached.

The number of centres involved in each country will be agreed upon in advance in consultation with the national coordinators who will have knowledge of clinical practices specific to each country. Follow up information will be collected for all patients after 12 months from the procedure. The “last patient last visit” should be conducted by the end of December 2013.

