3.4 POPULATION ENROLLED IN THE REGISTRY

3.4.1 Inclusion criteria

Enrollment and Follow-up: All consecutive Patients with indications for TLE (following HRS guidelines) in the participating Centres during the enrollment period will be included

3.4.2 Time of inclusion: the day before the procedure.

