3.5.5 Follow-up data

Twelve months follow-up is required to evaluate clinical failures of TLE procedures, endpoints and long-term complications.

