8 PROPOSED TIME PLAN

Executive-Steering Committee Meeting	December	2011
Final protocol and CRF	February	2012
Official launch at EHRA summit	March	2012
Start ethical committee process	July	2012
Start recruitment of patients	October	2012
Complete recruitment	June	2013
Results on baseline characteristics, in-hospital		
Outcomes and safety complications.	August	2013
Trial announcement during EHRA Europace	June	2013-4
Complete follow-up.	June	2014

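### The December 2013 last-visit date in section 3.1 contradicts the 12-month follow-up required of all patients and the June 2014 date in the time plan

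*Protocol*

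**What the plan says.** Three statements in Protocol section 3.1 bear on the point.

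- Recruitment: "The study should commence recruitment of patients in October 2012 and finish in June 2013". The section lets it continue beyond June 2013 if 3000 patients have not been enrolled by then.
- Follow-up: "Follow up information will be collected for all patients after 12 months from the procedure".
- Closing date: the last patient's last visit "should be conducted by the end of December 2013".

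Other sections fix the length of follow-up. Section 3.5.5 states: "Twelve months follow-up is required to evaluate clinical failures of TLE procedures, endpoints and long-term complications". Section 3.6.1 measures long-term clinical success at 12 months, and section 3.6.5.3 defines long-term complications and mortality as those within 12 months. The time plan in section 8 puts the end of recruitment in June 2013 and then lists "Complete follow-up. June 2014".

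**The concern.** The recruitment period, the 12-month requirement and the closing date in section 3.1 cannot all hold. A patient treated in June 2013 has a 12-month visit in June 2014, six months after the stated closing date. The extension clause makes matters worse, because a fixed calendar date cannot fit a recruitment period with an open end.

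The long-term half of the primary objective (section 3.2.1) is at stake, together with 12-month clinical success. Section 4 includes all enrolled patients in the analysis, and section 3.4.5 covers only withdrawal of consent and loss to follow-up before 12 months. A patient whose observation ended because the calendar ran out has no defined status. Someone working from section 3.1 alone could close follow-up early, and what was not observed then may not be recoverable later.

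**Working it through.** **Inputs**

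- Recruitment: October 2012 to June 2013 (sections 3.1 and 8), taken as 1 October 2012 to 30 June 2013.
- Follow-up: 12 months from the procedure, all patients (sections 3.1 and 3.5.5).
- Start of the clock: inclusion is "the day before the procedure" (section 3.4.2), so the enrolment date and the procedure date can be treated as the same.
- Stated last visit: 31 December 2013 at the latest (section 3.1).
- Planned enrolment: 3000 (section 3.1).
- Accrual pattern: not given. This is an assumption, varied below.

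**Step 1: can the stated date be reproduced?** Last visit = last procedure + 12 months = June 2013 + 12 months = June 2014. Section 3.1 says December 2013, so its date is not reproduced. Section 8 says June 2014, so its date is. The two sections differ by six months.

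**Step 2: who could reach 12 months by 31 December 2013?** Only patients treated on or before 31 December 2012. A patient treated on 30 June 2013 would have 184 days, about six months. This step needs no accrual assumption.

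**Step 3: what share of patients is that?** October to December 2012 has 31 + 30 + 31 = 92 days. January to June 2013 has 31 + 28 + 31 + 30 + 31 + 30 = 181 days. The total is 273 days. Let x = 92/273 = 0.337 be the fraction of the recruitment period before 1 January 2013.

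| Accrual (assumed) | Share treated after 31 December 2012 | Result | Of 3000 |
|---|---|---|---|
| Uniform | 1 − x = 181/273 | 66.3% | about 1,990 |
| Linear decline to zero | (1 − x)² | 44.0% | about 1,320 |
| Linear ramp-up from zero | 1 − x² | 88.6% | about 2,660 |

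**Step 4: sensitivity to the exact dates, uniform accrual.**

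- Start 1 October, end 1 June: (244 − 92)/244 = 62%.
- Start 31 October, end 30 June: (243 − 62)/243 = 74%.
- Recruitment extended to 30 September 2013: (365 − 92)/365 = 75%.
- Recruitment extended to 31 December 2013: (457 − 92)/457 = 80%.

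**Step 5: after correction.** With the last visit at 30 June 2014, no patient treated by 30 June 2013 is cut short.

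**The case against.** The best defence is that one sentence is out of line with several consistent ones. The December date is worded as a target, the sentence before it sets 12 months for all patients, and sections 3.5.5, 3.6.1, 3.6.5.3 and 8 agree with 12 months. It may simply be a stale date, and nothing shows that centres would follow it. That stands as far as it goes: the protocol does not show that follow-up will be truncated, only that one of its dates would truncate it. It does not make the date right. Section 3 speaks of follow-up of up to one year, which could be read as a maximum, but sections 3.1 and 3.5.5 turn 12 months into a requirement.

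A reader might infer more than the protocol supports:

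- **That two thirds of patients will lack 12-month data.** The 66% rests on uniform accrual, and any loss depends on the December date being followed.
- **That the 12-month rate is understated.** A crude proportion counting cut-off patients as event-free would be too low if late events occur. An estimate that handles censoring need not be. Section 4 fixes no method, and the protocol gives no late-event rate.
- **That comparisons between centres or countries are distorted.** This could happen for long-term outcomes if centres start at different times, but no centre start dates are given. Intra-procedural and pre-discharge outcomes are untouched.
- **That 12-month results would be reported too early.** The August 2013 report in section 8 covers baseline characteristics, in-hospital outcomes and safety complications. No early 12-month report is scheduled.

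**Conclusion.** The point holds. The December 2013 date contradicts the 12-month requirement in its own paragraph, section 3.5.5 and the time plan, and no reading reconciles them. It is more than a clerical slip, because the closing date decides whether the long-term part of the primary objective can be observed.

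It is certain, from the recruitment and closing dates alone, that patients treated from January to June 2013 could not complete 12 months by end December 2013. Their share is an assumption: about 66% under uniform accrual, about 44% to 89% across the accrual shapes tried, and larger if recruitment is extended. Incomplete 12-month measures follow if the December date is applied. The direction and size of any bias depend further on the analysis and on the late-event rate, neither of which the protocol gives.

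**What to change.** In section 3.1, replace the fixed date with a rule: *last patient last visit is 12 months after the procedure of the last enrolled patient (June 2014 if recruitment ends in June 2013), and moves with any extension of recruitment*. Align section 8 by tying its follow-up completion date to the same rule.

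The cost is a one-sentence correction in section 3.1 and a matching note in section 8. The last visit moves about six months later than section 3.1 now states, which section 8 already foresees.

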3.2 PRIMARY AND SECONDARY OBJECTIVES

3.2.1 Primary Objective

The primary objective is:

- to evaluate the acute and long-term safety of transvenous lead extraction.

Measures: major procedure-related complications (including deaths) in acute and long-term follow-up (see definitions in Chapt 3.6).

3.2.2 Secondary Objectives

The secondary objectives of the ELECTRa Registry are:

- To describe demographic, clinical, and biological characteristics of patients undergoing TLE procedure in a representative setting of European cardiology Centres.
- To describe the characteristics of leads undergoing extraction.
- To evaluate indications for TLE procedures.
- To describe the diagnostic and therapeutic approaches employed in the routine practice of physicians performing TLE procedures.
- To assess the acute and chronic outcomes (see definitions in Chapt 3.6) of TLE procedures.

The information collected in the Survey will permit a description of the European practice on TLE, a comparison of data among Centres and Countries, with possible evaluation of

- adherence to guideline recommendations,

- differences among small-medium-large volume Centres,
- experience-based outcomes,
- need of learning curve,
- timing and method of reimplantation after extraction.

- **3.2.3 Potential Value of the Registry**

Increased quality of care in the lead extraction process

Dissemination of knowledge

Verification and potential adjustment of standards for lead extraction procedures.

3.3 PARTICIPATING CENTRES

Centres will be enrolled on a voluntary basis from all the European Countries.

Centres will be anonymous and stratified on the basis of their volume of activity:

High volume Centres:	> 30 pts/y
Medium volume Centres	15>30 pts/y
Low volume Centres	< 15 pts/y

3.4 POPULATION ENROLLED IN THE REGISTRY

3.4.1 Inclusion criteria

Enrollment and Follow-up: All consecutive Patients with indications for TLE (following HRS guidelines) in the participating Centres during the enrollment period will be included

3.4.2 Time of inclusion: the day before the procedure.

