3.5.1 Pre Procedure Evaluation

To be filled out before the procedure, if lead extraction is planned

- Physical examination including height, weight, BMI, LVEF, NYHA Class, blood pressure.
- Concomitant cardiovascular disease including coronary artery disease, valvular heart disease, hypertrophic or dilated cardiomyopathy, congenital heart disease, previous sternotomy, chronic heart failure, electrical primary disease, other heart disease.
- Risk factors and concomitant diseases including hypertension, diabetes mellitus, chronic lung disease, chronic kidney disease.

- Cardiac Implantable Electronic Device history (Re-intervention, Upgrading, Replacements)
 - 12-lead electrocardiogram.
 - PA and LL Chest-X ray.
 - Transthoracic (+ TEE if systemic infection) echocardiography.
 - Laboratory tests.
 - Pharmacological treatment (antibiotics, anticoagulation, antiplatelets, antihypertensive and heart failure treatment).
 - Indications for Lead Extraction.

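### Sections 3 and 3.4.1 define the enrolled population differently; read literally, 3.4.1 screens out off-guideline extractions and fixes indication adherence at 100%

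*Protocol*

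**What the plan says.** Protocol section 3 sets the population without a guideline filter: "This is a prospective, multicentre, European Controlled Registry of consecutive patients undergoing TLE procedures in European Countries". It adds that consecutive patients are enrolled at each centre, and that "Indications to perform procedures will be left completely to the decision of participating physicians".

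Section 3.4.1, the rule a site would actually apply, reads: "All consecutive Patients with indications for TLE (following HRS guidelines) in the participating Centres during the enrollment period will be included".

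Section 3.2.2 lists among the secondary objectives "To evaluate indications for TLE procedures". After the objectives it says that the data will permit "a comparison of data among Centres and Countries, with possible evaluation of" several items, the first of which is "adherence to guideline recommendations".

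Section 2 gives the scope of those recommendations: the professional societies "have published recommendations describing indications, settings, facilities, training and accreditation for transvenous lead extraction procedures". Section 3.5.1 collects "Indications for Lead Extraction" before the procedure. Section 3.5.2 collects the number of personnel, surgical stand-by and presence, room setting, tools and techniques.

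**The concern.** The two sections disagree about one kind of patient: the one whose physician decides to extract for a reason that the HRS guideline does not cover. Section 3 puts that patient in the registry and section 3.4.1 does not, and the protocol has no rule that settles the matter.

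If 3.4.1 is followed literally, the sample is selected on a variable that the registry hopes to measure. Conformity of the indication with the guideline then carries no information, and the profile of indications lacks its off-guideline part. That part bears directly on a description of real-world European practice and on the stated hope of verifying and adjusting standards (section 3.2.3).

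This is a matter of eligibility, so it cannot be left to a statistical analysis plan: no analysis can recover patients who were never enrolled.

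**Working it through.** The point is mainly one of logic, so the texts come first and the arithmetic only illustrates it.

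**1. The plan's own figures.** The protocol gives no off-guideline share and no expected adherence, so there is no figure on this point to reproduce. Its one computed figure, about 1600 patients in section 4, concerns experienced versus less experienced centres. It is reproduced at 2% versus 5%, two-sided 5%, 90% power and equal groups: n per group = [1.960·√(2·0.035·0.965) + 1.282·√(0.02·0.98 + 0.05·0.95)]² / 0.03² ≈ 787, or 1574 in total. It does not depend on the inclusion wording.

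**2. The texts side by side.**

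| Patient | Section 3 | Section 3.4.1, literal |
|---|---|---|
| Extraction, indication follows HRS guideline | enrolled | enrolled |
| Extraction, indication outside HRS guideline | enrolled | not enrolled |

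**3. Consequence for adherence.** Let q be the share of TLE procedures whose indication lies outside the guideline. With all consecutive patients enrolled, indication adherence estimates 1 − q. Under a strictly applied 3.4.1, it equals 100% for every value of q. If some centres filter and others enrol everyone, the pooled estimate lies between 1 − q and 100%, at a point set by an unknown mix of site practice.

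**4. Size under assumed q.** All values of q are assumptions; 3000 is the planned enrolment in section 3.1.

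- Left out per 3000 procedures = 3000·q: 150 at 5% and 450 at 15%.
- Left out per 3000 enrolled = 3000·q/(1 − q): about 158 at 5%, 333 at 10% and 750 at 20%.
- Precision if all are enrolled, from (1 − q) ± 1.96·√(q(1 − q)/3000):

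| q | Adherence, all enrolled (95% CI) | Adherence under literal 3.4.1 |
|---|---|---|
| 5% | 95% (94.2-95.8) | 100% |
| 10% | 90% (88.9-91.1) | 100% |
| 20% | 80% (78.6-81.4) | 100% |

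A registry of this size would therefore measure indication adherence to within about 1.4 percentage points or better over this range.

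**5. Primary complication rate.** Take 2.5% in guideline-indicated patients (the midpoint of the 2-3% that section 4 gives for larger centres) and, as an assumption, twice that, 5%, in off-guideline patients. The overall rate is 2.5% + q·(5% − 2.5%): 2.6% at q = 5% and 2.9% at q = 15%, a shift of about 0.1 to 0.4 percentage points. The 95% half-width at 2.5% with 3000 patients is 1.96·√(0.025·0.975/3000) ≈ 0.56 points. This is an illustration and not a bound, since the protocol gives no complication rate for off-guideline patients.

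**The case against.** **Free choice of indication is not in conflict with an enrolment filter.** Section 3 governs the decision to extract and section 3.4.1 governs who is enrolled. A physician may extract off-guideline and simply not register the patient. This stands: a reader might infer that 3.4.1 restricts practice, but it does not. What remains is that section 3 also defines the enrolled population, and defines it more widely.

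**The objectives can still be addressed.** A reader might infer that the indication objective and the adherence evaluation become unanswerable. The documents do not support that. The mix of indications among enrolled patients, and its variation by centre and country, can still be estimated. Adherence is only a possible evaluation, and the recommendations also cover settings, facilities, training and accreditation; the section 3.5.2 data on setting, surgical cover and personnel are untouched. Only the indication component of adherence is fixed.

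**The parenthesis may be loose.** It could refer to how indications are classified. No eligibility check against the guideline is described, and section 3.4.3 does not exclude off-guideline indications. This is a fair reading and limits confidence, but the text does not state it. If it is the intent, a clarifying sentence is still needed. If the guideline grades indications, variation across grades would remain among enrolled patients, but the protocol describes no grades, and the contrast of inside versus outside would still be lost.

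**The CRF may already cover it.** Section 3.5 places the CRF and its definitions in an addendum not at hand, so an outside-guideline option may exist. It would be of little use while the inclusion criterion keeps such patients out.

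**Conclusion.** The point holds in limited form. Sections 3 and 3.4.1 define the enrolled population differently. If 3.4.1 is applied as written, indication adherence to the HRS guideline is 100% whatever the truth, and the indication profile is truncated. This rests on the literal reading of the parenthesis and on sites applying it.

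The number of patients lost cannot be derived from the protocol; the figures in the working depend on an assumed share.

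Two further inferences are tempting and not supported. One is that the primary complication rate would be materially distorted: nothing in the protocol shows a different rate in off-guideline patients, and even doubling it moves the overall rate by less than the sampling error in the illustration. The other is that centre and country comparisons would be biased by uneven use of the criterion: the ambiguity makes that possible, but neither its presence nor its size can be shown from the text.

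The correction is worth making because data lost at enrolment cannot be recovered later.

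**What to change.** Reconcile section 3.4.1 with section 3. Include all consecutive patients scheduled for or undergoing TLE at the centre during the enrolment period, whatever the indication. The word scheduled also keeps patients who refuse the procedure, whom section 3.5.5.1 expects to be followed up. Treat conformity with the HRS guideline, with an outside-guideline category, as a recorded variable and not as an entry filter, and report indication adherence from it. This concerns enrolment and recording only and leaves the decision to extract where section 3 puts it.

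The cost is one changed sentence and at most one CRF response option, since the indication is already collected. There are no added visits and no change to the sample size.

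If the sponsor does want a guideline-indicated population, section 3 should say so, and indication adherence should be removed from what section 3.2.2 offers to evaluate.

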3.4.3 Exclusion criteria

A. Patients unwilling or unable to give informed consent or unable to complete follow-up.

B. Psychological problems that might limit follow-up.

All patients (or legal guardians in case of patients unable to consent) are required to sign an informed consent form approved by the local ethical committee (according to national need)

3.4.5 Withdrawal from the study

Definitions of withdrawals from study:

Withdrawal of consent, Patient lost to follow-up before 12 months.

3.5 DATA COLLECTION

Data will be collected using a web based system.

The complete CRFs with the specifications and the definitions will follow in a dedicated addendum.

3.5.1 Pre Procedure Evaluation

To be filled out before the procedure, if lead extraction is planned

- Physical examination including height, weight, BMI, LVEF, NYHA Class, blood pressure.
- Concomitant cardiovascular disease including coronary artery disease, valvular heart disease, hypertrophic or dilated cardiomyopathy, congenital heart disease, previous sternotomy, chronic heart failure, electrical primary disease, other heart disease.
- Risk factors and concomitant diseases including hypertension, diabetes mellitus, chronic lung disease, chronic kidney disease.

- Cardiac Implantable Electronic Device history (Re-intervention, Upgrading, Replacements)
 - 12-lead electrocardiogram.
 - PA and LL Chest-X ray.
 - Transthoracic (+ TEE if systemic infection) echocardiography.
 - Laboratory tests.
 - Pharmacological treatment (antibiotics, anticoagulation, antiplatelets, antihypertensive and heart failure treatment).
 - Indications for Lead Extraction.

